8.2.1 Individual Discontinuation Criteria

- A participant may withdraw completely from the study at any time at his/her own request, or may be withdrawn at any time at the discretion of the investigator for safety, behavioral, compliance, or administrative reasons. This is expected to be uncommon. Stopping study intervention is not considered withdrawal from the study.
- At the time of discontinuing from the study, if possible, an early termination visit should be conducted, as shown in the Schedule of Activities ([Section 2](#)). See the Schedule of Activities (Section 2) for data to be collected at the time of study discontinuation and follow-up and for any further evaluations that need to be completed.
- The participant will be permanently discontinued from both the study intervention and the study at that time.
- If the participant withdraws consent for disclosure of future information, the Sponsor may retain and continue to use any data collected before such a withdrawal of consent.

8.3 Lost to Follow-up

The following actions must be taken if a participant fails to return to the clinic for a required study visit:

- All reasonable efforts must be made to locate participants to determine and report their ongoing status. This includes follow-up with persons authorized by the participant.
- Lost to follow-up is defined by the inability to reach the participant after a minimum of 3 documented phone calls, faxes, or emails, as well as lack of response by participant to 1 registered mail letter. All attempts should be documented in the participant's medical records.
- If the investigator's use of a third-party representative to assist in the follow-up portion of the study has been included in the participant's informed consent, then the investigator may use a Sponsor-retained third-party representative to assist site staff with obtaining the participant's contact information or other public vital status data, such as public health registries and databases, necessary to complete the follow-up portion of the study.
- The site staff and representative will consult publicly available sources, such as public health registries and databases, to obtain updated contact information.
- If, after all attempts, the participant remains lost to follow-up, then the last known alive date as determined by the investigator should be reported and documented in the participant's medical records.
- If it is determined that the participant has died, the site will use permissible local methods to obtain date and cause of death.

9 STUDY ASSESSMENTS AND PROCEDURES

- Study procedures and timing are summarized in the Schedule of Activities ([Section 2](#)).
- Protocol waivers or exemptions are not allowed.
- All immediate safety concerns must be discussed with the Sponsor immediately upon occurrence or awareness to determine if the participant should continue or discontinue intervention.
- Adherence to the study design requirements, including those specified in the Schedule of Activities (Section 2), is essential and required for study conduct.
- All screening evaluations must be completed and reviewed to confirm that potential participants meet all eligibility criteria before randomization. The investigator will maintain a screening log to record details of all participants screened and to confirm eligibility or record reasons for screening failure, as applicable.
- Procedures conducted as part of the participant's routine clinical management (eg, blood count) and obtained before signing of informed consent may be utilized for screening or baseline purposes provided the procedure meets the protocol-defined criteria and has been performed within the timeframe defined in the Schedule of Activities (Section 2).
- For several assessments, appropriate training will be provided to investigators and designated personnel at sites. Only those individuals trained and certified to perform these assessments will be performing them during the study.
- Repeat or unscheduled samples may be taken for safety reasons or for technical issues with the samples.

- As part of the online questionnaire (eCOA), the study Sponsor may collect and use information about the gender that participants identify with, sexual orientation, and intersex status. At the conclusion of the study, summaries of this information, including information already collected about race, ethnicity, and gender, across all study participants will be developed to understand the populations that participated in the study. In addition, in the future, this data may be combined with data from other BMS studies to conduct subsequent research on how the disease or treatments impacts certain populations. Answering the questions about the gender you identify with, sexual orientation, and intersex status is voluntary, and participants are not required to answer these questions in the questionnaire to take part in this clinical study.

9.1 Efficacy Assessments

Every effort must be made to ensure that the same evaluator(s) complete the assessment for each participant. If the evaluator(s) is/are unable to complete the evaluation, then a qualified individual with overlapping experience may perform the evaluation. Documentation of who performed the evaluation is to be recorded in source documents. Assessments are to be performed at approximately the same time of day throughout the duration of the study.

[figure not shown]
Baseline assessments must be performed per protocol (standard-of-care assessments may not be used for baseline). Procedures not specified in the protocol that are part of standard care may be performed if they do not interfere with study procedures; any data arising from such procedures are not to be reported in the eCRF.

9.1.1 Assessments used in both sub-protocols

9.1.1.1 Investigator-administered Assessments

[figure not shown]
9.1.1.1.1 Psoriasis Area and Severity Index (PASI)

The PASI is a measure of the average redness, thickness, and scaliness of psoriatic skin lesions (each graded on a 0 to 4 scale), weighted by the area of involvement (head, arms, trunk to groin, and legs to top of buttocks).²⁶ The PASI produces a numeric score that can range from 0 to 72, with higher PASI scores denoting more severe disease activity. The PASI can also be used to assess response to treatment. The PASI-50 is the proportion of participants who experience at least a 50% improvement in PASI score as compared with the baseline value. The PASI-75, PASI-90, and PASI-100 are defined similarly. BMS will host a training session prior to initiation of the study to demonstrate proper PASI scoring. All PASI assessments should be performed by a trained physician (dermatologist) or appropriately trained investigator who is experienced in the assessment of psoriasis patients.

9.1.1.1.3 Static Physician's Global Assessment (s-PGA)

The s-PGA is a 5-point scale of an average assessment of all psoriatic lesions based on erythema, scale, and induration.³⁰ The s-PGA measure determines psoriasis severity at a single point in time (without taking into account the baseline disease condition) as clear (0), almost clear (1), mild (2), moderate (3), or severe (4). All s-PGA assessments should be performed by a trained physician (eg, dermatologist) or appropriately trained investigator who is experienced in the assessment of psoriasis patients. Every effort should be made to ensure that the physician or designee who performed the s-PGA evaluations for a participant at randomization performs the s-PGA for that participant at all subsequent visits.

9.1.2 Palmoplantar Sub-protocol Specific Assessments

9.1.2.1 Investigator-administered Assessments

9.1.2.1.1 Palmoplantar Physician's Global Assessment (pp-PGA)

The pp-PGA is a 5-point scale of an average assessment of PP involvement.³⁴ The pp-PGA measure determines psoriasis severity at a single point in time (without taking into account the baseline disease condition) as clear (0), almost clear (1), mild (2), moderate (3), or severe (4). All pp-PGA assessments should be performed by a trained physician (eg, dermatologist) or appropriately trained investigator who is experienced in the assessment of psoriasis patients. Every effort should be made to ensure that the physician or designee who performed the pp-PGA evaluations for a participant at randomization performs the pp-PGA for that participant at all subsequent visits.

9.1.2.1.2 Palmoplantar-Psoriasis Area and Severity Index (pp-PASI)

The pp-PASI is an adaptation of the PASI grading system to evaluate the severity of PP (including the finger and toe surfaces) psoriatic lesions and their response to treatment.³⁵ The pp-PASI produces a numeric score that can range from 0 to 72.

The pp-PASI is divided into 4 regions: the right palm, the left palm, the right sole, and the left sole. Each palm contributes 20% and each sole contributes 30% to the total PP surface area. Each of these areas are evaluated for erythema, induration, and scaling, which are rated on a scale from 0-4. Each of these areas are evaluated for percent involvement and assigned a score based on a 0-6 scale. The pp-PASI should be performed by a dermatologist or appropriately trained investigator who is experienced in the assessment of psoriasis patients.

9.1.3 Genital Psoriasis Sub-protocol Specific Assessments

9.1.3.1 Investigator-administered Assessments

[figure not shown]
9.1.3.1.2 s-PGA of Genitalia (s-PGA-G)

The s-PGA-G is the clinician's determination of the participant's psoriasis lesions' overall severity in the genital area (labia majora, labia minora, and perineum in females; penis, scrotum, and perineum in males) at a given timepoint. Overall, lesions are categorized by descriptions for

elevation, erythema, and scaling.³⁹ It is not necessary that all 3 criteria be fulfilled. The s-PGA-G score is based on a combination of erythema and the secondary features (plaque elevation and/or scale). Since erythema is the most robust finding, it should be the dominant feature influencing the s-PGA-G rating in the majority of cases. For the analysis of responses, the patient's psoriasis is assessed as clear (0), minimal (1), mild (2), moderate (3), severe (4), or very severe (5). All s-PGA-G assessments should be performed by a trained physician (eg, dermatologist) or appropriately trained investigator who is experienced in the assessment of psoriasis patients. Every effort should be made to ensure that the physician or designee who performed the s-PGA-G evaluations for a participant at randomization performs the s-PGA-G for that participant at all subsequent visits.

9.1.3.1.4 Comprehensive Assessment of Psoriasis Patient (CAPP)– Genital Subindex Objective

Comprehensive Assessment of the Psoriasis Patient (CAPP) is a disease severity measure to assess the full burden of plaque psoriasis and subtypes, including inverse, scalp, nail, PP, and GenPs.⁴³ Only the genital subindex will be utilized for this study. Severity of genital areas involved by psoriasis (suprapubic area, perineum and in male: scrotum, penis; in female: labia major and/or minora) will be graded as 0 = clear; 2 = erythema, no raised plaques, no scale; 4 = erythema, mildly thick plaques, mild scale; 6 = erythema, moderately thick plaques, mild scale; 8 = prominent erythema, moderately thick plaques, moderate scale OR fissuring present; 10 = prominent erythema, thick plaques, hypertrophic scale with/without excoriations, irrespective of area involved OR skin tearing present. (For severity scores 2 to 8: +2 if labia minora or glans penis involvement). PROs of pain and intimacy would be evaluated using VAS (minimal score 0, maximum score 10). The final genital severity score = measured genital severity plus the higher of the 2 PRO VAS scores (minimal score 0, maximum score 20).

9.1.4 *Additional Assessments*

[Redacted]

[Redacted]

[Redacted]

9.2 Adverse Events

The definitions of an AE or SAE can be found in [Appendix 3](#).

AEs will be reported by the participant (or, when appropriate, by a caregiver, a surrogate, or the participant's legally acceptable representative).

The investigator and any qualified designees are responsible for detecting, documenting, and reporting events that meet the definition of an AE or SAE and remain responsible for following up on AEs that are serious, considered related to the study intervention or the study, or that caused the participant to discontinue before completing the study.

Refer to Appendix 3 for SAE reporting.

9.2.1 *Period and Frequency for Collecting AE and SAE Information*

All AEs and SAEs must be collected from the time of signing the consent, including those thought to be associated with protocol-specified procedures and until 30 days following discontinuation of dosing or participant's participation in the study if the last scheduled visit occurs at a later time.

The investigator must report any SAE that occurs after these periods and that is believed to be related to a study intervention or protocol-specified procedure.

- All SAEs will be recorded and reported to the Sponsor or designee, promptly and not to exceed 24 hours of awareness of the event, as indicated in Appendix 3.
- The investigator will submit any updated SAE data to the Sponsor or designee within 24 hours of updated information being available.

Investigators are not obligated to actively seek AEs or SAEs in former study participants. However, if the investigator learns of any SAE, including a death, at any time after a participant has been discharged from the study, and he/she considers the event reasonably related to the study intervention or study participation, the investigator must promptly notify the Sponsor.

The method of evaluating and assessing causality of AEs and SAEs and the procedures for completing and reporting/transmitting SAE reports are provided in Appendix 3.

9.2.2 *Method of Detecting AEs and SAEs*

AEs can be spontaneously reported or elicited during open-ended questioning, examination, or evaluation of a participant. Care should be taken not to introduce bias when collecting AEs and/or SAEs. Inquiry about specific AEs should be guided by clinical judgment in the context of known AEs, when appropriate for the program or protocol.

9.2.3 Follow-up of AEs and SAEs

- Nonserious AEs should be followed to resolution or stabilization, or reported as SAEs if they become serious (see [Appendix 3](#)).
- Follow-up is also required for non-serious AEs that cause interruption or discontinuation of study intervention and for those present at the end of study intervention as appropriate.
- All identified non-serious AEs must be recorded and described on the nonserious AE page of the CRF (paper or electronic). Completion of supplemental CRFs may be requested for AEs and/or laboratory test result abnormalities that are reported/identified during the study.

After the initial AE/SAE report, the investigator is required to proactively follow each participant at subsequent visits/contacts. All SAEs, [REDACTED], will be followed until resolution, until the condition stabilizes, until the event is otherwise explained, or until the participant is lost to follow-up (as defined in [Section 8.3](#)).

9.2.4 Regulatory Reporting Requirements for SAEs

- Prompt notification by the investigator to the Sponsor of SAEs is essential so that legal obligations and ethical responsibilities toward the safety of participants and the safety of a product under clinical investigation are met.
- An investigator who receives an investigator safety report describing SAEs or other specific safety information (eg, summary or listing of SAEs) from the Sponsor will file it along with the IB and will notify the IRB/IEC, if appropriate, according to local requirements.

The Sponsor or designee must report AEs to regulatory authorities and ethics committees according to local applicable laws and regulations. A suspected, unexpected serious adverse reaction is a subset of SAEs and must be reported to the appropriate regulatory authorities and investigators following local and global guidelines and requirements.

9.2.5 Pregnancy

This section is not applicable for Women Not of Childbearing Potential.

If, following initiation of the study intervention, it is discovered that a participant is pregnant or may have been pregnant at the time of study intervention exposure, including at least 30 days after study product administration, the investigator must immediately notify the Sponsor Medical Monitor/designee of this event and complete and forward a Pregnancy Surveillance Form to the Sponsor designee within 24 hours of awareness of the event and in accordance with SAE reporting procedures described in [Appendix 3](#).

In all cases, the study intervention will be discontinued immediately.

Follow-up information regarding the course of the pregnancy, including perinatal and neonatal outcomes and, where applicable, offspring information, must be reported on the Pregnancy Surveillance Form. Protocol-required procedures for study discontinuation and follow-up must be performed.

9.2.6 Laboratory Test Result Abnormalities

The following laboratory test result abnormalities should be captured on the Adverse Events – Nonserious and Serious Events CRF page. Paper forms are only intended as a back-up option when the electronic system is not functioning.

- Any laboratory test result that is clinically significant or meets the definition of an SAE.
- Any laboratory test result abnormality that requires the participant to have study intervention discontinued or interrupted.
- Any laboratory test result abnormality that requires the participant to receive specific corrective therapy.

It is expected that, wherever possible, the clinical rather than the laboratory term will be used by the reporting investigator (eg, anemia versus low hemoglobin value).

9.2.7 Potential Drug-induced Liver Injury

Wherever possible, timely confirmation of initial liver-related laboratory test result abnormalities should occur prior to the reporting of a potential DILI event. All occurrences of potential DILIs meeting the defined criteria must be reported as SAEs (see [Section 9.2](#) and [Appendix 3](#) for reporting details).

A potential DILI is defined as follows:

- Aminotransferase (ALT or AST) elevation $> 3 \times \text{ULN}$
AND
- Total bilirubin $> 2 \times \text{ULN}$, without initial findings of cholestasis (elevated serum alkaline phosphatase)
AND
- No other immediately apparent possible causes of aminotransferase elevation and hyperbilirubinemia, including, but not limited to, viral hepatitis, preexisting chronic or acute liver disease, or the administration of other drug(s) known to be hepatotoxic.

9.2.8 Other Safety Considerations

Any significant worsening of conditions noted during interim or final physical examinations, ECG, radiographic imaging, or any other potential safety assessment required or not required by the protocol should also be recorded as a nonserious AE or SAE, as appropriate, and reported accordingly.

9.3 Overdose

For this study, any dose of deucravacitinib greater than [REDACTED] within a 24-hour period will be considered an overdose. Overdoses that meet the regulatory definition of an SAE will be reported as SAEs (see [Appendix 3](#)).

In the event of an overdose, the investigator should:

- 1) Contact the Medical Monitor or designee immediately
- 2) Closely monitor the participant for AEs/SAEs and laboratory abnormalities for at least 5 half-lives of deucravacitinib, approximately 3 days.

Decisions regarding dose interruptions will be made by the investigator in consultation with the Medical Monitor or designee based on the clinical evaluation of the participant.

9.4 Safety

Planned timepoints for all safety assessments are listed in [Section 2: Schedule of Activities](#).

9.4.1 Physical Examinations

A complete PE will include general appearance, vital signs, eyes, ears, nose, mouth, throat, neck, respiratory, cardiovascular, respiratory, GI/abdomen, lymphatic, musculoskeletal, skin, psychiatric, and neurologic exams. A targeted PE will include any organ system associated with an AE or a laboratory abnormality.

[figure not shown]
While the targeted PE may not be as comprehensive as the initial full examination, key aspects should evaluate important body systems as clinically indicated. These body systems can include lymph nodes, liver, spleen, and breast at the discretion of the examiner. A targeted examination may note any changes in the participant's condition (body systems) since the last assessment and does not preclude examination of any of the other body systems as clinically indicated. Every effort should be made to ensure the same evaluator will complete the examination for each participant at all visits throughout the study. Documentation of who performed the examination is to be recorded in source notes.

9.4.2 Vital Signs

Vital signs include (ear or oral) body temperature, respiratory rate, and seated BP and heart rate and will be recorded at each visit based on Schedule of Activities (Section 2). BP and heart rate should be measured after the participant has been seated quietly for at least 5 minutes.

9.4.3 *Electrocardiograms*

A 12-lead ECG will be performed at the screening visit. The participant will remain supine for 5 to 10 minutes prior to the ECG and must have their lab work done after the tracing so that the ECG results remain as accurate as possible. The ECG results will be read by the primary study investigator or a designee.

[figure not shown]
9.5 Pharmacokinetics

Not applicable.

9.6 Immunogenicity Assessments

Not applicable.

9.8 Optional Future Research

This protocol will include residual sample storage for optional future research.

Samples kept for future research will be stored at the Sponsor-designated storage facility.

The manager of these samples will ensure that they are properly used throughout their usable life and will destroy the samples at the end of the scheduled storage period, no longer than 25 years after the end of the study or the maximum period allowed by applicable law.

Samples will be stored in a coded fashion, and no researcher will have access to the key. The key will be securely held by the investigator at the clinical site, so there is no direct ability for a researcher to connect a sample to a specific individual.

Further details of sample collection and processing will be provided to the site in the laboratory/procedure manual.

9.9 Health Economics OR Medical Resource Utilization and Health Economics

Health economics/medical resource utilization and health economics parameters will not be evaluated in this study.

10 STATISTICAL CONSIDERATIONS

10.1 Statistical Hypotheses

For the non-pustular PP psoriasis sub-protocol, the primary hypothesis is that the odds of achieving pp-PASI-75 at Week 16 in participants receiving deucravacitinib 6 mg QD are improved compared to participants receiving placebo.

The null hypothesis to be tested for the primary endpoint is the following:

- The odds of achieving pp-PASI-75 at Week 16 in participants receiving deucravacitinib 6 mg QD are the same as participants receiving placebo.

The null hypothesis corresponding to the key secondary endpoint is:

- The odds of achieving pp-PGA 0/1 at Week 16 in participants receiving deucravacitinib 6 mg QD are the same as participants receiving placebo.

For the GenPs sub-protocol, the primary hypothesis is that the odds of achieving s-PGA-G 0/1 at Week 16 in participants receiving deucravacitinib 6 mg QD are improved compared to participants receiving placebo.

The null hypothesis to be tested for the primary endpoint is the following:

- The odds of achieving s-PGA-G 0/1 at Week 16 in participants receiving deucravacitinib 6 mg QD are the same as participants receiving placebo.

The null hypothesis corresponding to the key secondary endpoint is:

- The mean change from baseline in GenPs Itch NRS score at Week 16 in participants receiving deucravacitinib 6 mg QD is not different from participants receiving placebo.

The null hypothesis corresponding to the second key secondary endpoint is:

- The odds of achieving s-PGA 0/1 at Week 16 in participants receiving deucravacitinib 6 mg QD are the same as participants receiving placebo.

[figure not shown]
Multiplicity Adjustment

[figure not shown]
The statistical comparisons for the primary efficacy endpoint and the key secondary endpoint will be carried out in a hierarchical order for each sub-protocol. The hierarchical testing will preserve the overall Type I error at 0.05 for each sub-protocol.

[figure not shown]
The primary endpoint for each sub-protocol will be tested with a 2-sided Type 1 error (α) of 0.05, and if statistical significance is met for the primary endpoint, testing will proceed with the 2-sided α of 0.05 passed down to each respective key secondary endpoint.

If statistical significance is not met for the primary endpoint, then subsequent p-values will be considered descriptive for that sub-protocol.

There will be no multiplicity adjustment for other additional endpoints in either sub-protocol; however, nominal p-values will be provided as descriptive statistics.

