- The odds of achieving s-PGA 0/1 at Week 16 in participants receiving deucravacitinib 6 mg QD are the same as participants receiving placebo.

The statistical comparisons will be carried out in a hierarchical order for each sub-protocol. The hierarchical testing will preserve the overall Type I error at 0.05 for each sub-protocol.

If statistical significance is not met for the primary endpoint, then subsequent p-values will be considered descriptive for that sub-protocol.

Data Monitoring Committee: No

A Data Monitoring Committee will not be used in the study.

Other Committee: Yes

This study will use an external Study Steering Committee.

Brief Summary:

The purpose of this study is to compare the efficacy of deucravacitinib to placebo for the treatment of participants with non-pustular palmoplantar or genital psoriasis.

The primary hypothesis for the non-pustular palmoplantar psoriasis sub-protocol is that the odds of achieving pp-PASI-75 at Week 16 in participants receiving deucravacitinib 6 mg QD are

improved compared to participants receiving placebo. The primary hypothesis for the genital psoriasis sub-protocol is that the odds of achieving s-PGA-G 0/1 at Week 16 in participants receiving deucravacitinib 6 mg QD are improved compared to participants receiving placebo.

The duration of study participation for both sub-protocols is approximately 60 weeks and will be divided into the following periods: screening (up to 4 weeks/28 days), treatment (52 weeks), and follow-up (4 weeks). Following the initial screening study visit, subsequent visits will occur at Day 1, Week 1, Week 2, Week 4, Week 8, Week 12, Week 16, Week 20, Week 24, Week 28, Week 32, Week 40, Week 52, and Week 56.

Participants who have completed the screening procedures and have met the inclusion/exclusion criteria for 1 of the sub-protocols will be randomized on Day 1 in a 2:1 ratio to either deucravacitinib 6 mg once a day or placebo, respectively, for the first 16 weeks. Participants with involvement of both sites during screening (genital and palmoplantar) can only be randomized to 1 of the sub-protocols as per investigator's discretion. At Week 16, all participants, regardless of their blinded intervention, will be switched to open-label deucravacitinib 6 mg QD bottles through Week 52. Participants and investigators will remain blinded to the double-blind study intervention from Day 1 to Week 16 until the end of the study.

Statement of expanded access: Not applicable

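### Genital psoriasis: the gate between itch NRS and s-PGA 0/1 is not written, so the stated rule does not by itself guarantee a Type I error of 0.05

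*Combined protocol and SAP*

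**What the plan says.** The Multiplicity Adjustment text in Section 10.1 makes an unconditional claim: "The hierarchical testing will preserve the overall Type I error at 0.05 for each sub-protocol". It describes the structure in the singular: "The statistical comparisons for the primary efficacy endpoint and the key secondary endpoint will be carried out in a hierarchical order for each sub-protocol".

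The operating rule has three parts:
- Start: "The primary endpoint for each sub-protocol will be tested with a 2-sided Type 1 error (α) of 0.05".
- Continue, if the primary is significant: "testing will proceed with the 2-sided α of 0.05 passed down to each respective key secondary endpoint".
- Stop: "If statistical significance is not met for the primary endpoint, then subsequent p-values will be considered descriptive for that sub-protocol".

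The synopsis (Section 1, Statistical Methods) repeats the claim and the same stop rule. It states the order more generally: "The statistical comparisons will be carried out in a hierarchical order for each sub-protocol".

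The number of key secondary endpoints differs between sub-protocols. Palmoplantar has one, pp-PGA 0/1. Genital has two: change from baseline in itch NRS, then s-PGA 0/1, which Section 10.1 introduces with "The null hypothesis corresponding to the second key secondary endpoint is". Table 10.4.1-2 also labels the s-PGA objective as second. Table 4-2 lists both under one key secondary heading and gives no testing order.

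**The concern.** The singular wording of Section 10.1 fits the palmoplantar sub-protocol. Applied to the genital sub-protocol, it leaves out one step: nothing readable in Section 1 or Section 10.1 makes the s-PGA 0/1 p-value descriptive when the itch NRS test fails. The only stated trigger for descriptive p-values among the ordered endpoints is failure of the primary.

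One result turns on this: primary significant, itch NRS not significant, s-PGA 0/1 significant. Under a fixed sequence, s-PGA 0/1 cannot be claimed. Under the literal rule it can. The result is plausible. Sections 3.3.3 and 5.5 report s-PGA 0/1 superiority over placebo in both Phase 3 trials, while Section 3.1 says that genital psoriasis has not been assessed with this drug. The handling of missing itch data is also unsettled: multiple imputation in Tables 10.3-2 and 10.4.3-2, baseline or last observation carried forward in Table 10.4.1-2. The sponsor is unblinded at the Week 16 lock (Sections 7.3.1 and 10.5), so the choice between readings should not still be open then.

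**Working it through.** **Inputs from the documents.** Claimed familywise error 0.05 per sub-protocol; primary tested at two-sided 0.05; two-sided 0.05 passed on after the primary; one palmoplantar and two genital key secondary endpoints (all Section 10.1).

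**Assumptions.** The readable text gives neither the correlation between the two key secondary test statistics nor the power for the primary. Correlations of 0 to 0.9 and primary power of 80%, 90% and near 100% are used to show the range.

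**Step 1. Reproduce the stated figure under a fixed sequence.** Order: s-PGA-G 0/1, itch NRS, s-PGA 0/1, each at 0.05, stopping at the first failure. A false claim requires rejection of the first true null in the order, and that has probability at most 0.05. Maximum familywise error = 0.05, as stated. A simulation of 2,000,000 draws with primary power near 100% gives 0.0497 to 0.0503 at correlations of 0 to 0.7.

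**Step 2. Literal rule: primary gate only, then both key secondaries at 0.05.** Take both key secondary nulls as true and primary power near 100%.
- Independent: 1 − (1 − 0.05)² = 1 − 0.9025 = 0.0975.
- Upper bound under any dependence: 0.05 + 0.05 = 0.10.
- Correlated: 1 − P(|Z1| < 1.96 and |Z2| < 1.96), bivariate normal:

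| Correlation | Familywise error |
|---|---|
| 0 | 0.0975 |
| 0.3 | 0.0951 |
| 0.5 | 0.0907 |
| 0.7 | 0.0835 |
| 0.9 | 0.0704 |

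**Step 3. Lower primary power.** With all three test statistics independent, multiply by the power:
- 80%: 0.80 × 0.0975 = 0.078.
- 90%: 0.90 × 0.0975 = 0.088.

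If the primary statistic is correlated with the other two as well, the excess shrinks. With a common correlation across all three, simulation gives:

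| Common correlation | 80% power | 90% power |
|---|---|---|
| 0.3 | 0.0717 | 0.0813 |
| 0.5 | 0.0615 | 0.0708 |
| 0.7 | 0.0484 | 0.0563 |

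**Step 4. Where the literal rule does no harm.**
- Primary null true: any false claim requires a false rejection of the primary first, so the error is at most 0.05.
- Primary effect real and only one key secondary null true: the error is at most the size of that one test, 0.05.
- Palmoplantar: with one key secondary, the rule is already a fixed sequence of two tests, so the error is at most 0.05.

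**The case against.** The strongest reply is that the plan means a fixed sequence. Both Section 1 and Section 10.1 call the testing hierarchical, alpha that is passed down is the language of a sequence, and s-PGA 0/1 is labelled second in Section 10.1 and Table 10.4.1-2. The continuation sentence follows one about the primary endpoint of each sub-protocol, so its reference to each respective endpoint may simply mean the endpoints belonging to that sub-protocol. On this reading the 0.05 claim is correct. It is probably the intent.

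A reader might therefore go too far and infer that the plan has chosen parallel testing, or that 0.05 is definitely lost. The documents do not support that. Nor do they support treating inflation as the usual case once the primary is positive: it needs both key secondary nulls to be true. The Phase 3 s-PGA 0/1 results at the same dose, in participants who here must enter with s-PGA of at least 3, make that configuration unlikely.

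What remains is the gap itself. Testing the primary first and then both key secondaries is also hierarchical, and it is what the operating sentence literally describes. An ordinal label numbers a hypothesis; it does not create a gate. A claim of error control has to hold for every combination of true and false nulls, including the unlikely one.

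Figures around the multiplicity text could not be read, and Section 10.4 leaves the SAP to be finalized before the Week 16 lock. Either may already state the sequence.

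**Conclusion.** The point stands as an unwritten gate, not as a proven loss of error control. The readable text supports two rules for the genital key secondaries. A fixed sequence delivers the stated 0.05. The literal primary-only gate does not guarantee it: familywise error is 9.75% in the worst case and roughly 7% to 9.5% over most of the other scenarios shown, falling to 5% or below when primary power is 80% and all three statistics are strongly correlated. These figures rest on assumed power and correlation and on both key secondary nulls being true with a real primary effect. The primary tests and the whole palmoplantar sub-protocol are unaffected. The practical exposure is narrow but decisive where it occurs: whether s-PGA 0/1 may be claimed after a failed itch NRS test.

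**What to change.** In Section 10.1, the synopsis and the SAP, before the Week 16 unblinding, write two sentences for the genital sub-protocol. First, the test order is s-PGA-G 0/1, then change from baseline in itch NRS, then s-PGA 0/1, each at two-sided 0.05. Second, testing stops at the first non-significant result, and every later p-value is descriptive, including that for s-PGA 0/1 after a failed itch NRS test. If an unreadable figure or the SAP already contains this sequence, align the protocol text with it.

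Maximum familywise error is then 0.05 under any correlation or power. The change follows the order already listed and needs no extra participants or data. Its cost is that s-PGA 0/1 can be claimed only if itch NRS is significant. If the sponsor does not want that dependence, Holm across the two key secondaries after the primary also keeps the error within 0.05 (simulated 0.043 to 0.049 with primary power near 100%), but the smaller of the two p-values must then meet 0.025.
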